Procedures and conditions that may contribute to IVH will be collected, such as: sepsis (positive blood culture, vasopressors, steroids, bolus administrations (fluids/meds), hypoglycemia (serum glucose <45) or hyperglycemia (serum glucose >200), hypercarbia (CO₂ >65mmHg), apnea/bradycardic episodes requiring stimulation, patent ductus

arteriosus, maximum respiratory support, suction events, line placements (PICC, IV, UAC/UVC) and/or needle punctures, UAC/UVC line collections, chest tube insertion, and any other noxious event

The subjects in both groups meet criteria for a standard of care head ultrasound at 6-8 days of life. Results from the head ultrasound report will be captured.

Clinical Outcomes Data – collected through date of discharge

The results of the last head ultrasound and/or magnetic resonance imaging (MRI) of the brain before discharge will be collected if these additional tests were ordered during the hospitalization (as solely determined by the attending neonatologist and not for study purposes).

Outcome data will include: days on mechanical ventilation throughout hospital stay, discharged home with G-Tube, discharged home on respiratory support (FiO₂, mode/settings), discharged with shunt, and length of stay (# days).

Adverse Event/Serious Adverse Event

The device, Turtle Midliner, solely impacts the skin contact areas. Only adverse events related to skin breakdown requiring wound care consultation with treatment will be reported as an adverse event. The principal investigator will evaluate adverse events related to skin integrity.

Any death will be reported as a serious adverse event according to Orlando Health IRB policy.

Major Protocol Deviation

For the purpose of this study, the midline position will be maintained with consistent use of the Turtle Midliner for all randomized study subjects in the treatment group (Turtle group) from ≤ 3 hours to 72 hours from birth. If the device is not utilized for a period greater than 30 consecutive minutes, the situation will be evaluated by the principal investigator. A major protocol deviation will be reported if the device was not in place for any reason other than the safety or well-being of the subject.

Study Endpoint

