The study period will be the first 72 hours of life with data collection for clinical outcomes to continue until discharge from the hospital, transfer to another institution, removal or withdrawal from the study, or death. There will be no additional contacts or follow-up for subjects beyond those time points.

The primary endpoint for the study is the difference in IVH incidence and severity between the two groups from birth through the first 72 hours of life.

5. Study Population

Each study subject must meet all of the indicated inclusion criteria and none of the exclusion criteria noted below:

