5.2 Exclusion Criteria

1. Presence of genetic/chromosomal abnormality, congenital hydrocephalus, congenital neuromuscular disorder, or other diagnosis determined to impact survival or generalizability of results
2. Unable to participate for any reason based on the decision of the principal investigator.
3. Infants born outside Winnie Palmer Hospital for Women and Babies

6. Study Duration/ Study Timeline

Projected start date approx. April 2018 following IRB approval)

- | | | |
|-----------|---|-----------|
| • Stage 1 | Enroll subjects following IRB approval through April 2020 | 24 months |
| • Stage 2 | Data analysis through July 2020 | 3 months |
| • Stage 3 | Poster, abstract and/or manuscript through January 2021 | 6 months |

7. Statistical Analysis Plan

Sample Size Determination:

A sample size of 142 neonates with 71 in each group (71 in control group and 71 in intervention group) was determined in order to achieve 80% power to detect a 20% difference in IVH between the two groups, using a target rate of IVH of 15% in the intervention group. The test statistic used was the two-sided Z test with pooled variance. The significance level of the test would be 0.05.

We aim to allow for an additional 5% in sample size to adjust for either voluntary or involuntary withdrawal of some of the enrolled subjects. Upon reaching 142 enrollees the data will be reviewed. If any baby (ies) within the first 142 enrollees was withdrawn, the baby will be replaced according to the original randomized group, up to an additional 8 babies to ensure the power of the study and maintain a balance between the groups. A maximum of 150 babies will be enrolled.

Data Analysis:

Data analysis will include descriptive statistics with means and proportions. Comparative statistics will be used to compare IVH outcomes in the two groups. IVH outcome will be

determined by a reduction in the rate and/or severity of IVH. Any additional information on data points may be described in tables and/or graphs.

8. Informed Consent Process

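### The IVH comparison has no place for infants who die, are transferred or are withdrawn before the 6-8 day head ultrasound; reporting IVH or death in all randomised infants is a cheap improvement

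*Combined protocol and SAP*

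**What the plan says.** - **Endpoint.** Section 4, Study Endpoint, gives the primary endpoint as the "difference in IVH incidence and severity between the two groups from birth through the first 72 hours of life".
- **Assessment.** Section 4, Data Collection, states: "The subjects in both groups meet criteria for a standard of care head ultrasound at 6-8 days of life". No other head imaging is expected for every infant. For later imaging, "The results of the last head ultrasound and/or magnetic resonance imaging (MRI) of the brain before discharge will be collected", and only if the attending neonatologist ordered it.
- **Death.** It has two operational roles. Under adverse events, "Any death will be reported as a serious adverse event". Under Study Endpoint, the plan provides for "data collection for clinical outcomes to continue until discharge from the hospital, transfer to another institution, removal or withdrawal from the study, or death".
- **Withdrawal.** Section 7, Sample Size Determination, allows "an additional 5% in sample size to adjust for either voluntary or involuntary withdrawal of some of the enrolled subjects". If any baby "within the first 142 enrollees was withdrawn, the baby will be replaced according to the original randomized group", with at most 8 replacements and a ceiling of 150.
- **Entry.** Section 5.2 excludes, among other conditions, any "other diagnosis determined to impact survival or generalizability of results".
- **Analysis.** Section 7, Data Analysis, promises descriptive statistics and a comparison of IVH outcomes between the two groups. It names no analysis set, no rule for a missing scan and no value for a death.
- **Background (section 2).** IVH nearly always arises within 72 hours of birth, and its neurologic consequences can be fatal.

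**The concern.** An infant must be alive and still in the study at 6-8 days to have the scheduled outcome. If infants without that scan drop out of the analysis, the trial compares survivors and not the groups that were randomised. The loss may be informative, because the protocol itself links IVH to death and care is unblinded. The bias has no fixed direction: it depends on how many infants die early in each arm and how many of them had IVH. Transfer and withdrawal before the scan leave the same gap.

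A further risk is that the rule gets chosen after the data have been seen. IVH is the trial's only objective, so there is no secondary result to fall back on.

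**Working it through.** **1. The plan's own figure.** Inputs from section 7: 15% IVH in the intervention group, a 20-point difference (so 35% in control, implied but not stated), two-sided pooled Z test, alpha 0.05, 80% power.

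n per group = [1.96 × √(2 × 0.25 × 0.75) + 0.8416 × √(0.35 × 0.65 + 0.15 × 0.85)]² / 0.20² = (1.200 + 0.501)² / 0.04 ≈ 72.4, so 73.

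The plan has 71. At 71 per group the power is 79.2% by the normal approximation and 80.4% by exact binomial calculation. The planned 142 therefore reproduces and is not in dispute.

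**2. Bias if only scanned infants are compared.** The documents give no early death rate, so these inputs are assumed: true IVH of 30% in both arms (no treatment effect), a proportion d who die before the scan, and a share q of those deaths who had IVH.

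Scanned-only IVH rate = (0.30 − d × q) / (1 − d)

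| q | d = 5% | d = 10% | Effect on the arm with more deaths |
|---|---|---|---|
| 0 | 0.300/0.95 = 31.6% | 0.300/0.90 = 33.3% | 1.8 points against |
| 0.3 | 0.285/0.95 = 30.0% | 0.270/0.90 = 30.0% | none |
| 0.5 | 0.275/0.95 = 28.9% | 0.250/0.90 = 27.8% | 1.2 points in favour |
| 1 | 0.250/0.95 = 26.3% | 0.200/0.90 = 22.2% | 4.1 points in favour |

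With deaths of 5% vs 7%, the range is 0.7 points against to 1.6 in favour. Equal death rates do not guarantee zero bias: at 5% in each arm, with q of 1 in one and 0.3 in the other, the rates are 26.3% and 30.0%.

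**3. Power if deaths are excluded and not replaced.** 71 × 0.95 = 67.5, so about 67 scanned per group and 77.5% power. 71 × 0.90 = 63.9, so about 64 and 75.8%. Both are exact binomial at 35% vs 15%.

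**4. Power of IVH or death before the scan.** Deaths are assumed equal in both arms and independent of IVH. Rate = d + (1 − d) × IVH rate.
- d = 5%: 0.05 + 0.95 × 0.35 = 38.25%, and 0.05 + 0.95 × 0.15 = 19.25%. Power at 71 per group is 72.1%.
- d = 10%: 0.10 + 0.90 × 0.35 = 41.5%, and 0.10 + 0.90 × 0.15 = 23.5%. Power is 64.1%.

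**5. An illustration with invented counts.** Take 71 per arm, with 22 control and 11 treated infants having IVH on the scan, and 4 and 7 earlier deaths. The pooled Z test gives:
- deaths excluded (22/67 vs 11/64): p = 0.039
- deaths counted as no IVH (22/71 vs 11/71): p = 0.029
- IVH or death (26/71 vs 18/71): p = 0.147

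**6. The 72-hour wording.** A scan at 6-8 days cannot date a bleed to before or after 72 hours. Expected IVH cases at the plan's rates are 71 × 0.35 + 71 × 0.15 = 35.5. If 5-10% of bleeds were late (assumed), that is 1.8 to 3.6 cases, spread over two arms that share the same scan.

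**The case against.** The strongest reply is that the effect is small and rests wholly on assumption. The 4.1-point figure needs one arm to have twice the deaths of the other and every death to have had IVH. Even then, with 67 vs 64 scanned and no true effect, the false-positive rate is about 8.5%; at the opposite extreme it is below 6%, against about 5% without bias. Power falls by only 3 to 5 points. In the invented example the two ways of analysing IVH alone agree; only the composite, which is a different endpoint, changes the conclusion. All of this stands, and it limits the weight of the point. It does not supply the missing rule.

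The entry exclusion does not supply it either. It concerns diagnoses, and infants enter within 3 hours of birth, so later deaths remain possible.

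A reader might infer more than the documents support:

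- **That deaths will be replaced as involuntary withdrawals.** Study Endpoint lists death apart from removal or withdrawal, which suggests the opposite. The text does not settle it. If deaths were replaced, the count would be restored but the outcome of the randomised infant would not.
- **That earlier scans in infants who die are not collected.** For such an infant, an earlier clinical scan may well be the last one and so be captured. The Head Ultrasound sheet (section 15.1) is not shown, so non-collection cannot be established.
- **That the 72-hour window invalidates the endpoint.** By the protocol's own account nearly all IVH occurs within it, so this is a wording mismatch.

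**Conclusion.** The point holds as a cheap improvement. No section says how an infant without a 6-8 day scan counts, and the natural default is a comparison of scanned survivors. Under the assumed 5% vs 10% deaths and 30% true IVH, the distortion lies between 1.8 points against and 4.1 points in favour of the arm with more deaths. It would be smaller if early deaths were fewer or more evenly split, provided the share of deaths with IVH were similar in the two arms.

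A reader might conclude that this bias could by itself produce the planned 20-point difference, or that the sample size is wrong. Neither follows: the bias is a fraction of 20 points under these assumptions, and the 142 reproduces.

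**What to change.** 1. **Section 7, Data Analysis.** Report IVH or death before the 6-8 day scan in all randomised infants, by randomised arm, beside the IVH incidence result. Label it supportive; its lower power (about 72% at 5% deaths, 64% at 10%) means that it should not replace the primary result.
2. **Section 7, Sample Size Determination.** State that death is not a withdrawal and is not replaced.
3. **Infants without a 6-8 day scan, for any reason.** Report counts by arm and reason (death, transfer, withdrawal). Bound the incidence result by counting all of them first as IVH and then as no IVH. These two analyses bound each arm's rate; they do not give the most extreme difference between arms. Record any earlier clinical head imaging, and use it under one rule, fixed in advance, for every randomised infant and not only those who die.
4. **Section 4, Study Endpoint (minor).** Name the 6-8 day ultrasound as the endpoint assessment and keep 72 hours as the treatment period.

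Ranking death as the worst severity grade is not recommended. An infant imaged without IVH who then died would be a non-case for incidence and the worst outcome for severity, within one joint endpoint.

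**Cost.** Wording in two sections, a check that earlier imaging is on the data sheet (one added item if it is not), and a little more analysis; no new procedure. A few late bleeds would be counted. Earlier imaging is ordered by unblinded clinicians, may differ by arm, and can miss a later bleed, so the bias is reduced and made visible but not removed.

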5.1 Inclusion Criteria

1. Gestational age less than or equal to 30 6/7 weeks at birth
2. Less than 3 hours from birth
3. Informed consent obtained from parent or legal guardian prior to reaching time point for randomization

5.2 Exclusion Criteria

1. Presence of genetic/chromosomal abnormality, congenital hydrocephalus, congenital neuromuscular disorder, or other diagnosis determined to impact survival or generalizability of results
2. Unable to participate for any reason based on the decision of the principal investigator.
3. Infants born outside Winnie Palmer Hospital for Women and Babies

6. Study Duration/ Study Timeline

Projected start date approx. April 2018 following IRB approval)

- | | | |
|-----------|---|-----------|
| • Stage 1 | Enroll subjects following IRB approval through April 2020 | 24 months |
| • Stage 2 | Data analysis through July 2020 | 3 months |
| • Stage 3 | Poster, abstract and/or manuscript through January 2021 | 6 months |

7. Statistical Analysis Plan

Sample Size Determination:

A sample size of 142 neonates with 71 in each group (71 in control group and 71 in intervention group) was determined in order to achieve 80% power to detect a 20% difference in IVH between the two groups, using a target rate of IVH of 15% in the intervention group. The test statistic used was the two-sided Z test with pooled variance. The significance level of the test would be 0.05.

We aim to allow for an additional 5% in sample size to adjust for either voluntary or involuntary withdrawal of some of the enrolled subjects. Upon reaching 142 enrollees the data will be reviewed. If any baby (ies) within the first 142 enrollees was withdrawn, the baby will be replaced according to the original randomized group, up to an additional 8 babies to ensure the power of the study and maintain a balance between the groups. A maximum of 150 babies will be enrolled.

Data Analysis:

Data analysis will include descriptive statistics with means and proportions. Comparative statistics will be used to compare IVH outcomes in the two groups. IVH outcome will be

determined by a reduction in the rate and/or severity of IVH. Any additional information on data points may be described in tables and/or graphs.

8. Informed Consent Process

The patient's parent or legal guardian will be approached by the principal investigator or sub-investigator and the study will be explained in clear, layperson language. All study procedures will be disclosed. Risks to the patient will be explained; no individual patient benefits will be promised. The patient's parent or legal guardian will be given the opportunity to ask questions and confer with family members and others. If the patient's parent or legal guardian elects to consent to the trial, he/she will sign and date the consent form.

The original signed form will remain with the investigator in the study file; a copy will be given to the parent or legal guardian and a copy will be filed in the official medical record as well.

9. Privacy and Confidentiality

Federal regulations at 45 CFR 46 111 (a) (7) requires that when appropriate, there are adequate provisions to protect the privacy of subjects and to maintain the confidentiality of data. To maintain confidentiality, only the study investigators and regulatory coordinator will have access to the case reports and subject records. All records will be kept in a locked, password-protected computer as well. All paper case report forms and source documents will be maintained in a secured area within a locked office and maintained for a minimum of three years after the completion of the study.

10. Risk/Benefit

This study involves a product, the Turtle Midliner, already on the market and available for commercial use for prevention of cranial asymmetry and head preference in infants 0 to 6 months of age. The product being evaluated is a breathable, cotton, Lycra and foam beanie device, with two positioning rolls. The Turtle Midliner has been in use in the WPH NICU since May 2016.

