3.2 Secondary Objectives

None

4. Study design/methodology

This study will be registered in Clinical Trials (clinicaltrials.gov) with the primary endpoint being a difference in IVH incidence and severity. We propose to conduct a randomized controlled trial in preterm infants (gestational age $\leq 30\ 6/7$ weeks) comparing the use of the Turtle Midliner and the standard of care practice (Control group). While blinding of study groups is always desirable in randomized studies, this will not be possible for this study.

Study Procedure

After eligibility of the infant is determined and the study informed consent is obtained from the parent or legal guardian, subjects will be randomized.

Randomization will follow a block randomization table that will determine if the infant will go into the group that will be positioned using the Turtle Midliner (Treatment Group) or not (Control Group).

All clinical care will be provided with consideration of the gestational age of the subject and follow NICU department guidelines and as ordered by physician and/or ARNP providers.

The key distinction for this study will be the use of the Turtle Midliner as a positioning aid in addition to standard of care for the Treatment Group, as opposed to solely standard practice of nesting and the use of rolls and other aids for the Control Group.

Treatment Group

The application and maintenance of the Turtle Midliner is within the scope of practice and skill-set of the NICU nursing and ancillary staff. The device has been in use in the WPH NICU since May 2016 when ordered by physician or nurse practitioner.

The use of the Turtle Midliner will be in addition to the NICU department process guidelines for positioning relevant to the gestational age of the subject. The Turtle Midliner will be applied no later than 3 hours following birth under the supervision of a

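### Allocation from a block table with no stated concealment or varying block size, combined with open investigator discretion over entry, leaves this unblinded single-site trial open to selection bias; for replacement infants the arm is fixed in advance by rule

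*Combined protocol and SAP*

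**What the plan says.** All references are to the combined protocol and SAP.

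- **Allocation (section 4, Study Procedure):** "Randomization will follow a block randomization table". The block size, whether it varies, who holds the table and how the next entry is hidden are not stated.
- **Blinding (section 4):** "While blinding of study groups is always desirable in randomized studies, this will not be possible for this study". Section 1.3 makes this a single-site trial, so there is one recruiting site.
- **Order of steps (section 4):** "After eligibility of the infant is determined and the study informed consent is obtained from the parent or legal guardian, subjects will be randomized". Section 5.1 likewise requires consent before randomization and entry within 3 hours of birth.
- **Discretion (section 5.2):** exclusion 2 covers an infant who is "Unable to participate for any reason based on the decision of the principal investigator". Exclusion 1 ends with a second open ground, "other diagnosis determined to impact survival or generalizability of results". Neither asks for a written reason, and the appendix list in section 15 has no screening log.
- **Who recruits and who sees the arm:** under section 8, "The patient's parent or legal guardian will be approached by the principal investigator or sub-investigator". Under section 4, a study investigator supervises application of the device.
- **Replacement (section 7):** after 142 enrolments, each withdrawn infant is replaced in the arm that infant had been assigned to, for up to 8 more infants and a maximum of 150.

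**The concern.** Three conditions for selection bias are present together: the recruiting team can see past assignments, the sequence is restricted by blocks, and those who recruit have wide discretion over who enters. When the end of a block can be worked out, an infant at high risk of IVH can be excluded, or the parents not approached, because of the arm that is due. The arms then differ in baseline risk before any treatment is given.

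Refused infants are never enrolled and no screening log is planned, so the pattern would be hard to detect or rule out afterwards. Section 7 plans no covariate adjustment, and section 4 no stratification, that would absorb such an imbalance.

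For replacement infants nothing has to be inferred. The arm is known before the infant is found, so these infants are not randomized in the ordinary sense.

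**Working it through.** **1. The plan's own figure.** Section 7 gives 71 per arm for 80% power, 15% IVH in the intervention arm and a 20-point difference (so 35% in controls), with a two-sided pooled Z test at 0.05. The mean rate is 0.25:

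n = [1.96·√(2·0.25·0.75) + 0.8416·√(0.35·0.65 + 0.15·0.85)]² / 0.20² = (1.2003 + 0.5015)² / 0.04 = 72.4, so 73 per arm.

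Power with 71 per arm is 79.2%. The stated figure is reproduced closely. It is not in dispute; it supplies the 35% rate and the 71 per arm used below.

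**2. Predictability.** Assume fixed 1:1 blocks of size 2b, with the size known and past assignments seen. The share of allocations that is certain beforehand is 1/(b+1).

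| Block size | Certain | Of 142 | Best guess correct |
|---|---|---|---|
| 2 | 1/2 = 50% | 71 | 75% |
| 4 | 1/3 = 33% | 47 | 71% |
| 6 | 1/4 = 25% | 36 | 68% |

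**3. Spurious effect when the device does nothing.** Assumptions, not given in the plan: 30% of infants are high-risk, overall IVH is 35%, and every high-risk infant is refused when the next slot is certain to be the device. Section 2 quotes about 45% IVH at 500-750 g, which is used as one high-risk rate. The other, 55%, is a pessimistic assumption.

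- Rate in the remaining infants: (0.35 − 0.30·0.45)/0.70 = 30.7%, or (0.35 − 0.30·0.55)/0.70 = 26.4%.
- Risk gap: 14.3 or 28.6 points.
- Among device slots, the share that is certain is again 1/(b+1), so the spurious reduction is δ = 0.30 × 1/(b+1) × gap.
- Two-sided type I error ≈ Φ(−1.96 + δ/SE) + Φ(−1.96 − δ/SE), with SE = √(2·p̄(1−p̄)/71) and p̄ = 0.35 − δ/2.

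| Block size | δ at 45% | Type I error | δ at 55% | Type I error |
|---|---|---|---|---|
| 2 | 0.30·0.50·14.3 = 2.1 | 5.8% | 0.30·0.50·28.6 = 4.3 | 8.5% |
| 4 | 0.30·0.333·14.3 = 1.4 | 5.4% | 0.30·0.333·28.6 = 2.9 | 6.5% |
| 6 | 0.30·0.25·14.3 = 1.1 | 5.2% | 0.30·0.25·28.6 = 2.1 | 5.8% |

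Example (block 2, 55%): p̄ = 0.329, SE = 0.0788, δ/SE = 0.544, and Φ(−1.416) + Φ(−2.504) = 0.078 + 0.006 = 8.5%. A simulation of 142 infants with 100,000 trials per setting agreed to within 0.2 point of type I error.

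**4. Partial refusal.** If half are refused, the high-risk share at certain device slots is 0.15/0.85 = 17.6%, a fall of 12.4 points instead of 30. Then δ = 0.124 × 1/(b+1) × gap, which is 0.4 to 0.9 points at 45% and 0.9 to 1.8 points at 55%. Simulated two-sided error is about 5.1% and 5.2 to 5.8%.

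**5. Replacements.** Up to 8/150 = 5.3% of infants have an arm set in advance, whatever the block size. If all 8 were device-arm infants chosen to be low-risk, δ would be 8/71 × 0.30 × gap = 0.5 points at 45% or 1.0 point at 55%.

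**The case against.** The strongest reply is that section 4 already has the steps in the right order, and section 5 requires each subject to meet no exclusion criterion. Exclusion 2, as worded, therefore gives no licence to remove an infant who has already been randomized. Discretionary exclusions are also ordinary, and with concealed, varying blocks this one would do little harm. Both points stand. The weakness is the undescribed allocation method together with the discretion, and deleting exclusion 2 alone would leave non-approach and exclusion 1 as routes to the same result.

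It is also true that predictability of the main sequence is inferred. The documents do not say that blocks are fixed, that recruiters know the size, or that the same individual recruits and fits the device. A reader might go further and infer that the table is open to the recruiting team, so that every allocation is known. Nothing in the documents says so; they are silent on concealment.

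Nor would selection leave no trace at all. Demographics and delivery history are collected at entry (section 4), so a large shift in risk could show as baseline imbalance. That helps only with enrolled infants. It cannot show who was turned away, or why.

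**Conclusion.** The point holds as a missing safeguard. The plan permits arm-dependent entry decisions and describes nothing that would prevent them, and for up to 8 replacement infants it fixes the arm in advance.

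The size is modest. With total refusal at certain device slots, the spurious reduction is about 1 to 2 points (high-risk IVH 45%) or about 2 to 4 points (55%), against a 20-point target. Two-sided type I error rises from 5% to about 5 to 6%, or about 6 to 9%. These figures rest on fixed blocks of known size, 30% of infants being high-risk, 35% IVH overall and systematic refusal; half refusal changes little.

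A reader might infer that exclusion 2 by itself biases the trial, or that selection took place in favour of the device. The documents support neither. They do not show that anyone selected, or which arm would gain. The case for acting is that the protection is cheap and the bias would be hard to exclude afterwards.

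**What to change.** - **Section 4:** use randomly varying block sizes that are not disclosed to those who recruit. Have the list prepared by someone outside the recruiting and bedside team. Release each allocation from sequentially numbered opaque sealed envelopes, or a locked electronic list, only after eligibility and consent are recorded and the infant is registered.
- **Section 5.2:** require a specific written reason for any exclusion under criterion 2, entered before allocation, and allow no discretionary exclusion after registration. A log of screened and excluded infants would let this be checked.
- **Section 7:** allocate replacement infants from the same concealed list, not to a predetermined arm.

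The cost is a short paragraph in each section, a regenerated list and one more line on the screening form. Envelopes or the electronic list must be reachable at all hours within the 3-hour window, which needs some organisation. Balance between the arms will be slightly less exact. The sample size stays at 142, with a maximum of 150.

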study investigator. The size/fit and application of the device will be according to the manufacturer's guidelines. The neutral midline head position, supine or slightly side-lying, with a bed elevation between 15° and 30° will be maintained during the first 72 hours of life. A member of the NICU physical therapy staff will perform and document a goniometry measurement (head/neck angle with head midline and perpendicular to shoulders, in line with the axial spine and not > than 5° deviation) a minimum of once daily during the first 72 hours of life and make any adjustments necessary, which is within their scope of practice.

Caregivers will document the NICU integrated flowsheet and the Sunrise electronic record with interventions regarding positioning, handling, skin assessment etc. per standard practice requirements.

The Turtle Midliner placement will be documented by clinical staff assigned to the subject's care every 2-4 hours on a tracking log. The active study period will end after the first 72 hours of life. The positioning device will be removed and the clinical care will continue according to NICU guidelines.

In the instance that phototherapy is ordered by the attending physician for babies in the treatment group, a compatible Turtle Midliner phototherapy eye shield will be used following manufacturer's size and guidelines.

Control Group

All clinical care for the control group will be within NICU department process guidelines relevant to the gestational age of the subject and as ordered by physician and/or ARNP providers. The neutral midline head position with the aid of nesting and/or rolls with a bed elevation between 15° and 30° will be maintained throughout position changes during the first 72 hours of life, which is standard practice. Caregivers will document the NICU integrated flowsheet and the Sunrise electronic record with interventions regarding positioning, handling, skin assessment etc. per standard practice requirements.

Data Collection

At Study Entry

Basic demographic information and delivery history will be collected.

Maternal Information- Only maternal information contained within the subject's record will be collected; the mother's record will not be accessed

Data collection will include: prenatal maternal conditions, maternal medications, mode of delivery, and delivery complications.

Clinical Data- collected from birth through the first 72 hours of life:

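### No covariate is planned for the IVH comparison; prespecifying adjustment for gestational age at birth would be a cheap improvement, though not a correction

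*Combined protocol and SAP*

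**What the plan says.** Section 7, Sample Size Determination, sets 71 infants per arm for 80% power to detect a 20% difference in IVH, with a target rate of 15% in the intervention arm and alpha 0.05. It adds: "The test statistic used was the two-sided Z test with pooled variance". The Data Analysis paragraph says: "Comparative statistics will be used to compare IVH outcomes in the two groups". It describes the outcome as "determined by a reduction in the rate and/or severity of IVH" and names no model and no covariate.

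Four other places bear on gestational age:

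- Section 2 says that the least mature infants carry the highest IVH risk.
- Section 5.1 admits infants with "Gestational age less than or equal to 30 6/7 weeks at birth" and sets no lower limit, so maturity will vary and is known for every infant before randomisation.
- Section 4, Study Procedure, says: "Randomization will follow a block randomization table that will determine if the infant will go into the group". It names no stratification factor.
- Section 4, At Study Entry, says: "Basic demographic information and delivery history will be collected".

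Section 4 also says of the design: "While blinding of study groups is always desirable in randomized studies, this will not be possible for this study".

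**The concern.** The plan itself identifies a strong candidate predictor of its outcome, and then uses it neither in the randomisation nor in the analysis. In a trial of 142 infants the arms can differ by chance in maturity. If they do, readers will ask whether maturity explains the IVH result. An adjustment chosen once the results are known answers that question poorly; one written down beforehand answers it well. Adjusting for a prognostic baseline variable also usually adds some power at the same sample size.

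The stakes are therefore how convincing and how precise the result is. The validity of the trial is not at issue.

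**Working it through.** **1. The plan's own figure.** Inputs from Section 7: 15% in the intervention arm, a 20% difference, 80% power, two-sided alpha 0.05. The control rate is not stated. Reading the difference as absolute gives 35%; a relative reading (18.75% vs 15%) would need 1565 per arm, so the absolute reading is clearly meant. The mean rate is 25%.

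n per arm = [1.960·√(2·0.25·0.75) + 0.8416·√(0.35·0.65 + 0.15·0.85)]² / 0.20² = [1.2003 + 0.5014]² / 0.04 = 72.4, so 73.

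The same formula gives 79.2% power at 71. Exact binomial enumeration of the pooled Z test gives 79.7% at 70 per arm and 80.4% at 71, so 71 is the smallest size that reaches 80%. The sample size reproduces.

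**2. Chance imbalance in maturity.** The documents give no spread of gestational age, so a range of SDs is assumed. The standard error of the difference in means is SD·√(2/71). At SD 1.9 weeks it is 1.9 × 0.168 = 0.319, and the probability of a difference of at least 0.5 week is P(|Z| ≥ 0.5/0.319 = 1.57) = about 12%. At SD 1.5 it is about 5%, and at SD 2.3 about 20%.

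**3. Power and type I error with adjustment.** Assumptions: 71 per arm, marginal rates of 35% and 15%, gestational age triangular from 22.5 to 31 weeks (mode 30, SD 1.9), and log-odds of IVH linear in weeks. The adjusted test in the table is the likelihood-ratio test for group in a logistic model with gestational age. There were 80,000 simulated trials per row for slopes 0 to -0.3, and 20,000 at -0.35.

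| Log-odds slope per week | Unadjusted Z | Adjusted | Change (points) |
|---|---|---|---|
| 0 | 80.5% | 80.4% | -0.1 |
| -0.1 | 80.4% | 80.5% | +0.1 |
| -0.2 | 80.3% | 81.3% | +1.0 |
| -0.3 | 80.3% | 82.5% | +2.2 |
| -0.35 | 80.2% | 83.3% | +3.1 |
| -0.5 | about 80% | about 86% | about +6 |

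For slopes 0 to -0.3, type I error was 4.9-5.0% unadjusted and 5.1-5.2% adjusted.

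**4. Does a standardised risk difference keep this power?** Yes. A second simulation used normally distributed gestational age and odds ratios of 1.0, 1.65, 2.7 and 4.5 per SD. The likelihood-ratio test had 80.8, 82.2, 86.2 and 90.0% power; the test of the standardised risk difference with a robust standard error had 80.7, 82.1, 86.0 and 89.8%. In the model of step 3, the 95% interval for the standardised difference covered 94.6-94.8% of the time at the design effect.

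**5. Which slope is plausible?** Section 2 gives 45% IVH at 500-750 g and 20% for very low birth weight infants overall in the late 1980s. These are birth-weight figures, so they are rough anchors only. Let 24 weeks stand for the 500-750 g group. Then 45% at 24 weeks with 35% overall (the derived control rate) implies a slope of about -0.11 per week, and 45% with 20% overall implies about -0.34.

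**6. Choosing between analyses afterwards.** For slopes 0 to -0.3, the Z test and the adjusted likelihood-ratio test fall on opposite sides of 0.05 in 1.5-5.5% of trials at the design effect and in 0.7-2.6% under no effect. Taking whichever is favourable would raise type I error to 5.3-6.4%.

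**The case against.** The strongest reply is that the Z test appears only as the basis for the sample size. The Data Analysis paragraph commits to no test, so the plan neither adopts an unadjusted primary analysis nor excludes an adjusted one. That stands. A reader might infer from the sizing sentence that the primary analysis is fixed as unadjusted; the documents do not support that. The absence of any named primary test is a larger gap, and the covariate is best written in when that gap is filled.

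Second, the endpoint combines incidence and severity without saying how, so a model for any IVH covers only part of it. That also stands. A binary logistic model does not carry over to four grades, and how the two components combine is a separate question.

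Third, the stakes are modest. Selecting the favourable test afterwards costs 0.2 to 1.2 points of type I error compared with the adjusted test alone (5.3 - 5.1 and 6.4 - 5.2), and at a slope of -0.1 the power gain is 0.1 point. This is fair at the low end. It does not show that the gain is negligible: the 45% figure implies a shallow slope only when paired with 35% overall, and a steep one when paired with the 20% that Section 2 also gives.

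Two supports are weak. The statement that "All clinical care will be provided with consideration of the gestational age of the subject" does not show that gestational age predicts IVH; only Section 2 says that. And choosing an analysis after seeing results is a risk in blinded trials too, so the open design adds only a little.

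**Conclusion.** The point holds as a low-cost improvement. The plan names gestational age as a driver of IVH, has it for every infant, and plans no use of it in the comparison.

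A reader might go further and infer that the unadjusted comparison is biased, or that the trial is too small without adjustment. Neither follows. Randomisation makes the unadjusted test valid (simulated type I error about 5%), and 71 per arm delivers the stated 80% power.

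The gain in power is about 0 points if gestational age is not prognostic, +2 to +3 points at slopes of -0.3 to -0.35 per week, and about +6 points at -0.5, which is steeper than either Section 2 anchor implies. The direction is secure. The size rests on the assumed slope and spread of gestational age, which the documents do not give, and it applies to IVH as yes/no only. The more dependable benefit is a prespecified answer if the arms differ in maturity.

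**What to change.** In Section 7, Data Analysis, before any comparison of IVH by arm, state that:

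- The incidence comparison is adjusted for gestational age at birth, as a continuous variable in weeks.
- One result governs: the gestational-age-standardised risk difference from a logistic model of any IVH on randomised group plus gestational age, with its 95% confidence interval (robust or influence-function standard error) and the matching two-sided 0.05 test. This keeps the difference in rates on which the trial was sized, whereas the model's odds ratio is conditional on gestational age and answers a different question.
- The unadjusted pooled Z test is reported as supportive.
- Any severity comparison is adjusted for gestational age with a model suited to ordered grades. How incidence and severity combine is to be settled separately.
- The events recorded over the first 72 hours (Section 4, Clinical Data) are not used as covariates in this analysis, because they can arise after randomisation.

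The cost is a short paragraph and a slightly less simple analysis, with about 0.1 point of power lost if gestational age is not prognostic. No new data, extra infants or change to randomisation is needed.
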